A subject participating in the post-study open-label placebo subject procedure administration period will be required to:

- ✓ continue his or her required abstinence from use of non-study related medications and therapies for the relief of foot pain and the as-needed consumption of the study rescue medication (OTC Tylenol) for his or her foot pain, through to the end of the open-label placebo subject procedure administration period;
- ✓ record the same measures as during the initial procedure administration phase, as follows:

DAILY MEASURES

The subject will record the required information in the Subject Daily Diary, as applicable, at home.

FOLLOWING EACH PROCEDURE ADMINISTRATION

Within 10 minutes following administration of each of the post-study open-label procedure administration period 12 study procedure administrations with the Erchonia® FX-635™, the subject will record the following at the test site:

- Visual Analog Scale (VAS) Degree of Pain Rating
- Adverse Events Evaluation

FOLLOWING COMPLETION OF THE PROCEDURE ADMINISTRATION PHASE: AT THE TEST SITE

The post-study open-label procedure administration period final evaluation visit will occur at the test site within one hour following completion of the 12th and final open-label procedure administration with the Erchonia® FX-635™.

The following measures will be recorded at this visit:

- Visual Analog Scale (VAS) Degree of Pain Rating
- Neuropathic Pain Symptom Inventory (NPSI)
- Subject Satisfaction With Foot Pain Level
- Adverse Events Evaluation

Following completion of the final post-study open-label test site evaluation visit, a subject's participation in the post-study open-label placebo subject procedure administration period will be complete. Subjects participating in the post-study open-label procedure administration phase will not be required to enter a post-procedure evaluation phase.

TABLE OF SUBJECT EVENTS

The following table provides a progressive summary of subject events throughout this study.

| PRE-PROCEDURE ACTIVITIES |
|--|
| 
➤ A potentially well-suited and interested candidate for participation in the study attends the investigator's office.➤ The investigator reviews the informed consent form with the candidate.➤ A candidate who voluntarily signs the informed consent form will be randomly assigned to procedure group and enter the study qualification evaluation phase of the study. |
| PRE-PROCEDURE WASHOUT PHASE: 48 HOURS |

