An adverse event (AE) is defined as any unfavorable and unanticipated sign (including an abnormal laboratory finding), symptom, or disease temporally associated with the use of a study procedure(s), whether or not it is related to the study procedure(s). The intensity of all AEs is classified as follows:

- *Mild*: A mild AE is defined as an event characterized by "awareness of symptoms which are easily tolerated."
- *Moderate*: A moderate AE is defined as an event in which "sufficient discomfort is present to cause interference with usual activity."
- *Severe*: A severe AE is defined as an event characterized by "extreme distress causing significant impairment of function or incapacitation."
- A *Serious Adverse Event (SAE)* is any AE occurring at any dose that results in:
 - Death.
 - A life-threatening event.
 - Inpatient hospitalization or prolongation of existing hospitalization.
 - Persistent or significant disability/incapacity.
 - Congenital anomaly/birth defect.

In addition, an important medical event that may not result in death, be life-threatening, or require hospitalization may be considered a SAE when, based on appropriate medical judgment, it may jeopardize the individual and/or may require medical or surgical intervention to prevent one of the outcomes listed above.

An *Unexpected AE* is any AE of which the specificity or severity is not consistent with that expected or anticipated as possible from administration of the study procedure.

A *Reasonably Related AE* is one that is possibly probably or definitely related to the study procedure (as determined by the study investigator).

REASONABLY ANTICIPATED AND POTENTIAL ADVERSE EVENTS

SAEs are not anticipated to occur in this clinical study.

Reasonably anticipated and potential AEs that may occur in this clinical study include the following:

- *Anticipated Adverse Event*: None observed or reported to date in prior clinical trials.
- *Potential Adverse Events*: include skin irritation, itching, discoloring, rash, indentations, pain/discomfort and infection.

EVALUATION OF ADVERSE EVENTS

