At each evaluation and procedure administration test site visit throughout the clinical study, and at any other time throughout the duration of the clinical trial that is necessary, evaluation for the occurrence of any potential adverse event will occur. This includes any observations made by the study investigator or other study staff or any reports made by the subject. Subjects will be instructed as to what constitutes an adverse event and how to report any potential adverse event(s) he or she may identify during study participation to the test site. The subject will be instructed to formally evaluate for potential adverse events through their recordings in their Subject Daily Diary completed at home.

RECORDING OF ADVERSE EVENTS

AEs that occur after randomization are recorded by the Principal Investigator on the AE page of the CRF. Recording is done in a concise manner using standard, acceptable medical terms. Any clinically significant changes in pre-existing conditions (based on medical history/physical examination results) are recorded on the CRF AE pages.

REPORTING OF ADVERSE EVENTS

The investigator will notify the Sponsor right away of any identified or reported adverse event, whether determined by the investigator to be related or unrelated to the study treatment or device or whether it is an anticipated or unanticipated AE. The investigator and the Sponsor will determine if the AE is a promptly reportable event to the governing IRB. The investigator will formally report any serious, life-threatening, or unexpected adverse experiences, including death that occurs within the duration of this study regardless of the relationship to the study procedure.

PROTOCOL DEVIATIONS AND VIOLATIONS

Both protocol deviations and protocol violations are accidental or unintentional changes to, or non-compliances with, the IRB-approved research protocol without prior sponsor and IRB approval. The difference between the two lies in the level of risk introduced by the change.

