Positive blinding efficacy will be supported by comments provided to support perceived group allocation that pertain to the determination being made based on treatment efficacy or lack thereof; e.g.: 'My foot pain is much less than it used to be, so I believe I got the real treatment' or 'My foot pain hasn't really changed, so I believe I got the fake treatment.'

Blinding will be determined to have failed if comments provided to support perceived group allocation pertain to factors such as sensation/visual clues (e.g. I saw/didn't see a light go on the laser, etc.) or other factors that pertain to blinding having been compromised such as 'I overheard the doctor saying I wasn't getting the real treatment.'

SAFETY ANALYSES

Safety analyses will be based on all subjects who were randomized to test or placebo procedure group. Safety will be assessed by evaluating and comparing frequency and incidence of observed and/or reported adverse events between test and placebo procedure groups related to administration of the Erchonia® FX-635™ laser procedures. A chi-square test with a continuity correction will be performed to compare the percentage of subjects who experienced adverse events between test and placebo procedure group subjects.

INDIVIDUAL SITE ANALYSIS

Analysis of results will be performed by individual test site and pooled across test sites. Application of a balanced test-control group study design incorporating a varied block by test site randomization procedure will contribute to statistical justification of pooling data across the different test sites.

INFORMED CONSENT

- Informed consent will be an agreement between the individual investigator and each subject, having the capacity to understand and make an informed decision. Consent will be obtained prior to each potential subject's participation in this clinical study.
- Each subject participating in this clinical study will be made aware of the fact that his or her participation involves research and the intent of the research, the expected duration of his or her participation and a description of the procedures that will be followed.
- Each subject will be made aware of the reasonably expected benefits he or she might receive, as well as any risks or potential discomfort that are involved.
- Each subject will also be made aware of alternative treatments available to him or her.

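### The AE definition contradicts the protocol's own AE rules, and the safety set has no treatment condition while the time of randomization is stated inconsistently

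*Combined protocol and SAP*

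**What the plan says.** **Definition.** Under Adverse Events Definition, an AE is "any unfavorable and unanticipated sign", symptom or disease linked in time with a study procedure, related to it or not. The same section defines an Unexpected AE as a kind of AE.

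**Listed events.** The next section opens: "Reasonably anticipated and potential AEs that may occur in this clinical study include the following". Its line for anticipated events reads "None observed or reported to date in prior clinical trials". Its line for potential events says that they "include skin irritation, itching, discoloring, rash, indentations, pain/discomfort and infection", which makes seven types.

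**Reporting.** Under Reporting of Adverse Events, the investigator notifies the sponsor of any AE, related or not, and regardless of "whether it is an anticipated or unanticipated AE".

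**Safety set.** The Safety Analyses section states: "Safety analyses will be based on all subjects who were randomized to test or placebo procedure group". It names no treatment condition. The intent-to-treat efficacy set, under Statistical Methods, does require receipt of the first procedure.

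**Time of randomization.** In the Table of Subject Events, a candidate who signs consent "will be randomly assigned to procedure group and enter the study qualification evaluation phase". The Randomization section likewise has the investigator ask the sponsor for the assignment once consent is signed. The Subject Group Randomization section instead randomizes a subject who is fully qualified. Under Confirmation of Qualifying VAS Rating, a subject whose two-day washout mean is below 50 leaves the study before any procedure.

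**The concern.** A definition of an AE decides what enters the safety data. If being unanticipated is a condition, an event that the sponsor foresaw can be ruled out at the first step, before the reporting rule applies, because that rule covers only events already identified or reported as AEs. Subjects are taught what counts as an AE and keep a diary at home, so the definition could shape what they write down.

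The safety set raises a second question. AE percentages are meant to describe people exposed to the device. If subjects are assigned at consent and some then fail qualification or the washout check, they add to the denominator but almost nothing to the numerator. Both arms' percentages fall, and so does the difference between them. The efficacy set guards against this; the safety set does not.

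**Working it through.** **Part 1: the definition (comparison of text, no arithmetic)**

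| Place | Can an anticipated event be an AE? |
|---|---|
| Adverse Events Definition, opening sentence | No: being unanticipated is a condition |
| Same section, Unexpected AE | Yes: unexpected AEs are a subset, so expected ones exist |
| Reasonably Anticipated and Potential Adverse Events, opening sentence | Yes: all the events introduced are called AEs |
| Reporting of Adverse Events | Yes: the rule covers both kinds |

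The opening sentence conflicts with the three other places.

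Whether it reaches the seven listed types depends on whether *potential* implies *anticipated*. The list keeps the two labels apart and names no anticipated event. The Unexpected AE definition, however, applies the word *anticipated* to what is merely possible from the procedure. Both readings are open.

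**Part 2: the denominator**

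*The plan's own figure.* The only stated number that bears on the safety denominator is the sample size. With 55% against 20%, two-sided alpha 0.05, power 0.80 and pooled variance (mean proportion 0.375):

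n = [1.96 × √(2 × 0.375 × 0.625) + 0.8416 × √(0.55 × 0.45 + 0.20 × 0.80)]² / 0.35² = 28.8, rounded up to 29.

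29 / (1 − 0.083) = 31.62, rounded up to 32 per arm. The plan's figures reproduce. The documents give no AE rate and no number randomized but untreated, so what follows is illustration.

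*Formula.* Let N be the number randomized in an arm and u the number never treated. Assume that untreated subjects contribute no AE. This is reasonable because the definition requires a link in time with a study procedure, and the safety comparison concerns events related to the laser procedures. Then

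reported rate = rate among treated × (N − u) / N.

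*Numbers, with N = 32 and assumed values of u:*

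| u | Treated | Factor | True 10% reads | True 20% reads |
|---|---|---|---|---|
| 0 | 32 | 1.000 | 10.0% | 20.0% |
| 1 | 31 | 0.969 | 9.7% | 19.4% |
| 3 | 29 | 0.906 | 9.1% | 18.1% |
| 5 | 27 | 0.844 | 8.4% | 16.9% |
| 8 | 24 | 0.750 | 7.5% | 15.0% |

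The plan speaks of 64 qualified subjects. If the 32 per arm counts only those, the untreated come on top and the factor is 32 / (32 + u). With u = 3 this is 32/35 = 0.914, and a true 20% reads 18.3%.

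*Effect on the comparison.* Take 7 against 1 subjects with an AE (assumed) and the planned continuity-corrected chi-square test:

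| Denominator per arm | Rates | Risk difference | Risk ratio | p |
|---|---|---|---|---|
| 32 (all randomized, 8 untreated) | 21.9% vs 3.1% | 18.8 points | 7.0 | 0.059 |
| 24 (treated only) | 29.2% vs 4.2% | 25.0 points | 7.0 | 0.053 |
| 29 (treated only, had 3 been untreated) | 24.1% vs 3.4% | 20.7 points | 7.0 | 0.057 |

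The risk difference shrinks by the factor in the previous table (18.8 / 25.0 = 0.75). With equal shares the risk ratio does not move, and the p-value hardly does. With unequal shares the risk ratio is multiplied by the ratio of the two arms' factors.

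**The case against.** A reader might infer that the definition removes the seven listed reactions and that harm is therefore understated. The documents do not support either statement.

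- The protocol labels the seven types potential and names no anticipated event. On those labels, none of the seven fails the unanticipated condition.
- The Evaluation of Adverse Events section tells subjects how to report potential events and has them use the diary for these. It also requires an evaluation at every procedure and evaluation visit at the site, including what staff observe. Capture does not rest on subjects applying the definition alone.
- The consent text and case report forms are not in the material available, so nothing shows that subjects are told to disregard foreseeable events.
- Nor do the documents show that the listed reactions are the events most likely to come from the device; they report none in earlier trials.
- Subject Group Randomization requires full qualification first. If that includes the washout check, treatment follows within an hour of the pre-procedure measures, and the untreated share would be close to zero.
- Even with a quarter of each arm untreated, the example test result barely changes.

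Most of this stands, and it limits the point to a contradiction and a risk. It does not remove the point. The definition is still at odds with three other places, and the use of *anticipated* for what is only possible keeps the narrower reading open. The qualified-subjects sentence is contradicted by the event table and fits poorly with the Randomization section, so it cannot be relied on to keep untreated subjects out of the safety set.

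**Conclusion.** Two drafting faults hold.

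1. The AE definition contradicts the rest of the AE text and can be read to leave out foreseeable reactions, including the seven listed as potential. The effect on AE counts cannot be derived from the documents.
2. The safety set admits never-treated subjects if randomization follows consent. Each arm's AE percentage and the risk difference are then lowered by the untreated share: about 3% relative for 1 of 32, 9% for 3 of 32 and 25% for 8 of 32. The share is an assumption throughout. It is zero if everyone randomized is treated. The figures also assume no AEs in untreated subjects, and the unchanged risk ratio assumes equal shares in the two arms.

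That harm will be understated is a possibility, not a finding.

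**What to change.** - In Adverse Events Definition, delete the words that require the event to be unanticipated. Keep anticipated/unanticipated only as a classification of recorded AEs.
- In Safety Analyses, define the safety set as all subjects who received at least one procedure, analysed by the device actually received. The protocol's own examples of violations include a placebo subject given active treatment, so the second half of this rule is needed.
- Reconcile Randomization, Subject Group Randomization and the Table of Subject Events on when assignment occurs relative to qualification and the washout check. Report the number randomized but never treated in each arm.

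The cost is wording in the protocol and analysis plan. A few more mild events may be recorded, and the safety denominator may be slightly smaller. Nothing in the treatment of subjects changes.
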